10.7. Exploratory analyses

The impact of treatment may vary across LAs where there is heterogeneity in how they handle the proactive support calls or in the effectiveness of the downstream services they refer participants to. To address this quantitatively, we will build on the main analysis model with interaction terms to arrive at a model of best fit (treatment*LA to explore differential treatment impact by LA, treatment*risk to explore differential treatment impact by baseline risk, and risk*LA to explore differences across LAs in the relationship between predicted risk and actual subsequent homelessness). We will also carry out exploratory treatment*LA interaction models and subsample analyses with no Risk indicator so they can include Test Valley. We will carry out additional descriptive analyses on key findings relating to differential delivery by the LAs arising from the IPE.

As a test of the validity of the predictive model, we will also compare the predicted baseline risk of homelessness in the control arm (which will experience BAU support) to actual subsequent homelessness. We will apply the same model specification as the main analysis but excluding the treatment allocation variable (which is redundant as we are only considering the control group). As in the main analysis, we will trial both probit and logit link functions. If the households sampled for Test Valley have a reasonable spread across Xantura's risk tiers then we will also attempt to repeat this analysis with Test Valley but substituting a Tier indicator for the Risk Score indicator.

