6. TARGET POPULATION

6.1. Eligibility

The target group for this research is the population of households at risk of homelessness within the next 3-6 months, across the four LAs participating in this trial (see **5.3 Research Setting**).

Eligibility criteria

Households will be deemed 'at risk' according to a predictive model run by Xantura. The model generates a household-specific risk score (0-100) indicating the expected likelihood of the household becoming homeless in the next three to six months under BAU conditions. Any household with a score greater than or equal to 50 is considered 'at risk' and is eligible for the trial unless they meet one of the exclusion criteria set out below.

Exclusion criteria

Households who meet any of the following exclusion criteria will not be eligible, regardless of risk score:

- They are already participating in a CHI trial
- They ask not to receive the intervention
- They ask for their data not to be used in this trial
- They are already receiving intensive support from LAs via a Relief or Prevention Duty issued in the last 6 months

- They have already been identified in OneView by London Borough of Barking and Dagenham's Homes and Money hub and are receiving targeted support (this team is already using the OneView model to provide targeted support)

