6.4. Trial Flow Diagram

7. OUTCOME MEASURES

7.1. Primary Outcome

Definition

The primary outcome is a household-level binary variable indicating whether any household member is owed a relief duty as a result of a homelessness application made by or for any household member between the trial's start and the 9-month follow-up. There are two ways in which a homelessness application can result in a relief duty:

1. The application resulted in a '[relief duty](#)' being issued for that household.
2. The application resulted in a '[prevention duty](#)' which ended before the 9-month follow-up because the household or any household member became homeless.

Issuing a relief duty means the housing authority deems a household to already be homeless and accepts the duty to take reasonable steps to help the applicant secure accommodation. Issuing a prevention duty means the housing authority deems a household at risk of homelessness and accepts the duty to take reasonable steps to help prevent that. Those found to be homeless at the end of a prevention duty are consequently owed a relief duty.

Why is it measured

To determine whether the intervention achieves its ultimate aim of reducing homelessness among the target population.

Data source

Aggregated from Homelessness Case Level Information Classification ('H-CLIC') records, via the OneView platform.

When is it measured

At the 9-month follow-up.

For whom is it measured

All households enrolled in the trial.

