8. DATA COLLECTION

8.1. Data collection methods

All study outcomes and planned covariates come from administrative records, which will be provided by LAs on a monthly basis and collated within the OneView platform. Additionally, call handlers will use OneView to record their attempts and success at making the treatment calls to support the compliance analysis and IPE. Xantura will have responsibility for managing data collection, ensuring data quality, and minimising missing information. They will provide household-level risk scores for the randomisation and then will deliver outcome data at the 2-month and 9-month follow-ups.

Timelines

For each batch, the trial will begin with randomisation, followed by a 1-month intervention period in which LAs deliver the calls to treatment households, with the two follow-up data collection points occurring 2 and 9 months after the end of the intervention period.

Table 6: Data collection procedures and assessment timeline

Assessment point	Type of data	Data collection approach
Pre-trial Batch 1: April 2025 Batch 2: May 2025 Batch 3: June 2025	Baseline characteristics of the sample All administrative data from LAs Risk scores from Xantura's predictive model (for randomisation)	Data collected from LA records by Xantura via OneView
1-month Intervention period Batch 1: May 2025 Batch 2: June 2025 Batch 3: July 2025	Outcomes related to the proactive call made to individuals in at risk households.	Data collected from LA call handlers by Xantura via OneView
2-month follow-up Batch 1: July 2025 Batch 2: August 2025 Batch 3: September 2025	Secondary outcome data	Data collected from LA records by Xantura via OneView

9-month follow-up Batch 1: February 2026 Batch 2: March 2026 Batch 3: April 2026	Primary outcome data Secondary outcome data	Data collected from LA records by Xantura via OneView
---	--	---

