10.2. Descriptive statistics

We will report descriptive statistics on:

- Sample size and attrition at the trial's start, the 2-month follow-up, and the 9-month follow-up
- Predicted baseline risk scores across arms at the trial's start, the 2-month follow-up, and the 9-month follow-up (to assess balance)
- Variables for underlying risk factors used to develop the predicted baseline scores
- The primary outcome at the 9-month follow-up (the full distribution as well as summary statistics – mean, mode, standard deviation)
- All secondary outcomes at the 2-month and 9-month follow-ups
- Whether and when treatment arm households received the call
- Whether and when households were issued a prevention duty
- Whether and when households were issued a relief duty

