- 4-8x 45 min interviews with support service teams (1-2 from each LA) (mid-delivery) depending on each LA set up
- 4x 30 min interviews with residents (1 per LA) who did not engage with the proactive call (mid-delivery, either by video or phone call)
- 28x 45 min interviews with residents (7 per LA) who engaged positively with the call (16 mid-delivery directly after the call/12 post-delivery after receipt of some support service, either by video or phone call)

We will also explore the predictive power of Xantura's model on actual homelessness outcomes over the course of the trial period in the absence of the intervention using data from the Control group. We will first analyse all LAs together using a generalised linear model with logit link function, in which the dependent variable is the primary measure of homelessness and the predictors are main effects for baseline risk and LA. To explore the possibility that the predictive model is more accurate in some LAs than others, we will also carry out an additional analysis including an interaction term between LA and baseline risk.

Focus groups with CHI and Xantura staff

Method, sampling and recruitment

We will conduct focus groups with the CHI delivery team and Xantura staff at the scoping and post-delivery stages. We will work with the project leads within CHI and Xantura to identify the most appropriate members of staff who understand the context and have been involved in selecting the LAs and the set-up of the intervention.

Data collection: sources and processes

We will develop semi-structured topic guides that ensure consistent coverage of points that require examination, but allow space for spontaneous responses to questions which would be leading if asked directly. Focus groups will be conducted by trained and experienced researchers; all will follow a project-specific risk and safeguarding procedure. All interviews/groups will be conducted online. Interviews will be video-recorded and transcribed however all transcriptions will be anonymised removing all personal identifiable information.

Data quality, assurance and confidentiality

All video recordings will be stored securely and destroyed within 3 months of completion of the research project. All personal identifiable information will be removed from the transcripts. Transcripts will be stored using a unique code given by the research team. All transcripts will be stored securely and access will be restricted to the research team only.

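### The validity test of the predictive model sets a 3-6 month risk score against about 10 months of outcome, and its regression can show ranking but not whether the stated probabilities are right

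*Protocol*

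**What the plan says.** Section 6.1 defines a 0-100 score "indicating the expected likelihood of the household becoming homeless in the next three to six months under BAU conditions". It also sets the entry threshold: "Any household with a score greater than or equal to 50 is considered" at risk. Footnote 3, attached to Figure 3 in section 9.3, treats the score as an absolute probability. If the model works as stated, at least half of the identified households should become homeless; no time window is given.

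The primary outcome in section 7.1 is a relief duty owed following an application "made by or for any household member between the trial's start and the 9-month follow-up". Section 8.1 places that follow-up. Each batch has one month for the calls after randomisation, and the clock is then set: "with the two follow-up data collection points occurring 2 and 9 months after the end of the intervention period".

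Section 10.7 then plans the validity test: "we will also compare the predicted baseline risk of homelessness in the control arm (which will experience BAU support) to actual subsequent homelessness". It reuses the primary model of section 10.3 without the treatment term, with logit and probit links. Section 11.2 describes the same analysis for the process evaluation: "the dependent variable is the primary measure of homelessness and the predictors are main effects for baseline risk and LA". It adds only a risk-by-LA interaction. Separately, section 10.2 lists descriptive statistics that include baseline scores, the primary outcome and "Whether and when households were issued a relief duty".

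**The concern.** There are two separate mismatches between the test and what it is meant to test.

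The first is the horizon. A probability defined over 3-6 months is compared with events accumulated over a longer period. Any statement about absolute accuracy, including the 50% benchmark in footnote 3, then depends on how many events fall after month six.

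The second is the form of the model. Section 10.3 enters the raw score with a free coefficient, a free intercept and LA dummies. If every stated probability is too high by a common factor on the odds scale, the intercept moves and the score coefficient hardly changes. Because the score enters as 0-100 and not as a log-odds, a coefficient of 1 is not a calibration target either.

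At stake is IPE question 7, which asks how well the model predicts homelessness without the intervention. It also bears on the first Theory of Change assumption, that the model has useful predictive value. Authorities deciding whether to adopt the approach will read the answer as evidence about the tool.

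**Working it through.** **Step 1: length of the outcome window.** Section 8.1 gives a 1-month call period plus 9 months: 1 + 9 = 10 months from randomisation. Table 6 agrees: batch 1 is scored in April 2025 and followed up in February 2026, which is 10 months. The score's horizon is 3-6 months. Neither 10.7 nor 11.2 cuts the outcome at 3 or 6 months.

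**Step 2: what the window does to an absolute comparison.** The documents give no hazard shape, so a constant hazard is assumed. A risk P over h months becomes 1 − (1 − P)^(10/h) over 10 months.

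- P = 50% at 6 months: 1 − 0.5^(10/6) = 68.5% at 10 months.
- P = 50% at 3 months: 1 − 0.5^(10/3) = 90.1% at 10 months.

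In reverse, starting from 50% observed at 10 months:

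- At 6 months: 1 − 0.5^(6/10) = 34.0%.
- At 3 months: 1 − 0.5^(3/10) = 18.8%.

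The result depends on the hazard. If every event fell by month six, 50% at 10 months would also be 50% at 6 months, and the gap would vanish. With front-loaded risk the six-month figure lies between 34% and 50%; with a rising hazard it would be below 34%.

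**Step 3: what the specified regression can detect.** Test Valley has no risk score, so three LAs remain: 3 × 500 = 1,500 randomised, 750 controls, and 750 × 0.8 = 600 after the protocol's 20% attrition. The model logit(p) = b0 + b2·Risk + LA dummies was simulated with 600 controls and 400 replicates. Scores were assumed uniform on 50-95, with true log-odds equal to logit(score/100) plus a constant shift. Mean predicted risk is 72.5% throughout.

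| Shift | Observed rate | Odds ratio per 10 points | AUC |
|---|---|---|---|
| 0 | 72.5% | 1.72 | 0.69 |
| −1 | 51.7% | 1.76 | 0.70 |
| −2 | 30.8% | 1.82 | 0.71 |
| −3 | 15.3% | 1.89 | 0.71 |
| −3.5 | 10.3% | 1.92 | 0.71 |

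The Risk coefficient was significant in every replicate of every row. Results with 750 controls were the same to within 0.01 on the odds ratio. In the last row predicted risk is 72.5 / 10.3 = 7.0 times the observed rate, yet the score coefficient and AUC look no worse than under perfect calibration. The score distribution is an assumption, but the absorption of a uniform shift by the intercept is not: it follows from the form of the model.

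**Step 4: can calibration be estimated with this sample?** At an observed rate of 50%, the 95% half-width with 600 controls is 1.96 × √(0.25/600) = 4.0 percentage points. With 600/3 = 200 per LA it is 1.96 × √(0.25/200) = 6.9 points. A gap of the size in Step 2 (50 − 34 = 16 points) would be visible overall and by LA.

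**The case against.** A reader might infer that the planned test will certify an over-predicting model as accurate, in the model's favour and by 16 points. The documents do not support that.

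- The 16-point figure concerns an absolute comparison. Sections 10.7 and 11.2 set no pass mark and plan no calibration verdict, so it applies to a reader's use of footnote 3 and not to the regression coefficient. The effect of the longer window on that coefficient has not been quantified.
- The direction is not established. The score predicts homelessness, whereas the outcome requires an application that leads to a relief duty, or a prevention duty that fails. Homelessness without an application is not counted, and section 9.2 expects some households to leave the area. Both push the observed rate down.
- Gross miscalibration would not stay hidden. Section 10.2 reports scores and outcomes, and section 11.2 reports score distributions by LA. A mean score of 72.5 beside a 10% event rate would be noticed.
- Section 2.1 says the model is not the subject of the evaluation, and the analysis is exploratory.
- Calibration statistics could be left to a statistical analysis plan.

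The first four points stand and limit the finding. The last stands only in part, because the protocol itself fixes the dependent variable and the regression for this test, and that stated choice is the issue. The descriptives are not linked to the test or to a 3-6 month window, and two unquantified biases in opposite directions do not make the comparison sound.

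**Conclusion.** The point holds as a limitation of an exploratory analysis. The test compares a 3-6 month probability with about 10 months of outcome, and its regression measures ranking, not the accuracy of the stated probabilities. The window effect can be large in an absolute comparison: 50% at 10 months matches about 34% at 6 months or 19% at 3 months under a constant hazard, and less of a gap if risk is front-loaded. The narrower outcome definition works against this, so the net direction of error is unknown. The claim about the regression rests on its free intercept and not on the simulated score distribution. The primary treatment estimate is untouched. What is affected is the answer to IPE question 7 and any later reading of the 50% benchmark.

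**What to change.** In sections 10.7 and 11.2, for the control arm of the three scored LAs, add a validity outcome cut at 6 months after the score date, and a second at 3 months, built from the relief-duty dates that section 10.2 already plans to report. Against it, report:

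- observed rate against mean predicted risk, overall, by LA and by score band, with confidence intervals;
- calibration intercept and slope from a logistic regression on logit(score/100), with a stated rule for any score of exactly 100, where the logit is undefined;
- AUC, noting that selection at 50 or above, highest scores first, restricts the range and so limits it.

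Keep the 9-month analysis alongside as description, and give footnote 3 a time window.

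State the downsides. Duties recorded late may be missed at a 6-month cut, particularly those following a failed prevention duty. Section 10.2 lists when duties were issued but not when a prevention duty ended; the primary outcome definition needs that timing, so its availability in the extract should be confirmed. A relief duty also remains narrower than homelessness, whatever the cut.

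The cost is a short wording change and a few lines of code, with no extra sample and, subject to that confirmation, no new data. It should be settled before analysis starts, which Table 5 puts at May 2026.

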10.8. Missing data

Description of Missing Data Patterns

The trial's reliance on existing administrative data means the risk of data being missing on a large scale is generally low. The predictor variables in our specified

analyses must be present for a household to be enrolled in the trial, so the only variables in which missing data should be possible are our outcome measures. We will describe the extent of missingness of all primary and secondary outcomes; overall, by arm, and in each LA.

Following CHI's Statistical Analysis Guidance, in the event of any missing data we will seek to establish why (the mechanism) and the pattern of missingness. To do so, we will run a binary logistic regression to regress an indicator of missingness on the treatment dummy variable and blocking variables used in our primary analysis. A statistically significant effect of treatment would indicate that data are 'missing experimentally not at random' (MENAR), i.e., there is evidence of differential loss of data across the trial's arms, which might be a source of bias.

If any of the blocking variables are statistically significant, then the data is not 'missing completely at random' (MCAR). The blocking design used in the randomisation balances treatment and control across LAs and levels of predicted baseline risk, so evidence that outcomes are not MCAR is not necessarily indicative of bias. In this case, we would re-run the primary analysis without the blocking variable and if the results are similar then a complete-case analysis is unlikely to be biased.

Handling Missing Data

For less than 5% missingness overall in our primary/secondary outcome we propose a complete-case analysis. Likewise, if the treatment dummy variable is not significant then data are 'missing experimentally at random' (MEAR) and a complete case analysis is appropriate.

Where outcomes are MENAR, we will explore several methods to reduce bias. The imputation methods preferred in CHI's guidance are not possible, since they depend on baseline measures that won't be present in this study. Instead, we will trial and report on each of the following:

- Excluding any blocks containing missing data from the primary analysis
- Introducing additional household-level covariates to see if conditioning on them eliminates the statistically significant effect of treatment on the likelihood of missingness, and then repeating the primary analysis with those covariates included.
- Three approaches to imputing outcomes: using those from other cases within the same block and testing the extremes of imputation by replacing all missing values with 1s or all with 0s.

Attrition at the LA level

In the event of data being missing from an entire LA because that LA withdraws from the trial, imputation would not be possible and that LA would be excluded from all analyses.

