5.2. Study Design

Study design details

The IE is a two-arm parallel RCT with randomisation at the household level, blocked by LA and predicted risk of homelessness. Households in the 'treatment' arm will receive proactive support (in the form of a phone call) from their LA in addition to BAU support. Households in the 'control' arm will only receive BAU support from LAs. This varies between LAs and refers to the range of activities that LAs and local organisations (including the third sector) undertake, and services they offer, to prevent and reduce homelessness. This support is available to households in both

the intervention and control arms, the difference is whether they receive a phone call that signposts them to the relevant support for them.

Allocation

Verian will randomly allocate households into the trial's two arms with equal probability, with a blocking design to ensure that the sample within each LA is as well balanced as possible on predicted risk of homelessness at the trial's start.

To assign blocks, we will independently sort each LA's sample by a continuous risk score generated by Xantura and then sequentially allocate households to blocks of four, following the sorted order. The target sample size at this point will be a multiple of four, so all blocks should be fully filled. If this is not the case, any remaining households will be entered into the final block. Once sorted into blocks, we will randomly assign households within each block so that every block of four contains two treatment households and two control. If the final block contains an odd number of households, we will randomise those households freely. The sample is thus stratified by LA and then risk score within LA.

We will randomise using the R package 'randomizr' (Coppock, 2019). One researcher will conduct the randomisation, but the code will be checked by another researcher to ensure it has been conducted correctly and can be reproduced. Once conducted, the randomisation code will be saved and made available in the OSF pre-registration that will be published for this trial.

Batching

We will deliver the sample to LAs in three batches, at the start of the first, second, and third months of the trial. We will run the randomisation separately for each batch, using up-to-date risk scores generated by Xantura.

Update to protocol: Study design in Test Valley

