10.3. Primary Analyses

Analytical approach

The primary analysis will estimate the effect of treatment on the likelihood of a successful homelessness application being submitted by or on behalf of any individual within a sampled household, on an intent-to-treat (ITT) basis. We plan to apply a parsimonious model with treatment as the predictor of interest, and two baseline covariates used in the blocking design of the randomisation.

The analysis will take the form of a generalised linear model with a logit link function to accommodate the binary measure used for the primary outcome. To improve power, we will cluster standard errors at the block level.

The model will follow this specification:

$$\text{logit}(p(Y_i = 1)) = \beta_0 + \beta_1 \text{Treat}_i + \beta_2 \text{Risk}_i + \beta_3 \text{LA}_i$$

Where:

- $p(Y_i = 1)$ is the probability that the i^{th} household ($i = 1, \dots, n$, where n is the number of households) submitted a successful homelessness application (or had one submitted on their behalf) during the trial period,
- $Treat_i$ is a binary variable for treatment allocation (0 = Control, 1 = Intervention),
- $Risk_i$ is the continuous risk score generated for that household that was used in the pre-trial randomisation,
- LA_i is a vector of binary dummy variables representing the Local Authority the household is in (0 = non-member, 1 = block member).

This approach to the primary analysis cleanly reflects the study's design to maximise power without conditioning on additional covariates that could complicate the interpretation of the model's results. Alternative approaches would be to explicitly represent the blocking design through a vector of dummy variables (instead of separate indicators for risk and LA) in a conditional logistic regression or to drop all covariates and use treatment as the sole predictor. We will follow both of these approaches as sensitivity analyses.

We will report uncertainty through confidence intervals at p-values. For the treatment effect, we will report p-values continuously as well as a binary indication of whether the treatment effect is statistically significant.

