10.6. Sensitivity Analysis

Alternative analysis methods

To test the robustness of the trial's main findings to different analysis methods, we will repeat the primary analysis introducing several variations.

Firstly, we will re-run the primary model using a probit link function instead of a logit, per CHI's Statistical Analysis guidance. This analysis tests whether the trial's results hold under an alternative and equally justifiable approach to that taken in the primary analysis.

Secondly, we will trial an alternative analysis in which the indicators for LA and baseline risk are replaced with a vector of dummy variables representing the blocks to which households were assigned. This analysis would be a conditional logistic regression, which is better suited to handling many small strata that do not gain precision as the study's sample size increases (since the stratum size remains constant at 4 households). This analysis captures the impact of treatment in the event that predicted risk scores vary in predictive power across LAs.

And thirdly, we will repeat the main analysis but dropping all predictor variables apart from treatment. This approach is likely to lose power, but if in practice the baseline risk scores of households recruited into the trial are generally high and with little variation, then the loss may be minimal. We will run this analysis both including and excluding cases from Test Valley.

Compliance analysis (CACE)

To complement the primary ITT analysis, we will also conduct Complier Average Causal Effect (CACE) analysis to provide a more accurate measure of treatment efficacy amongst 'compliers'. We will apply the instrumental variables approach using the Two Stage Least Squares (2SLS) method.

For a household in the treatment arm to be considered 'compliant', the following must be true:

- The LA call handler successfully made telephone contact with an adult member of the household
- They were able to complete the treatment call (i.e., they were not cut off prematurely)
- If any member of the household submitted a homelessness application within the trial period, the call took place before that application was made.

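### Similar results with and without risk score and LA do not show that complete-case analysis is unbiased (Protocol 10.8)

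*Protocol*

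**What the plan says.** Under its description of missing-data patterns, section 10.8 regresses an indicator of missingness on treatment and the blocking variables. If a blocking variable is significant, the data are taken not to be missing completely at random. The plan notes that "The blocking design used in the randomisation balances treatment and control across LAs and levels of predicted baseline risk", and will then "re-run the primary analysis without the blocking variable and if the results are similar then a complete-case analysis is unlikely to be biased". It gives no scale or cut-off for similarity.

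The rules on handling come next in the same section. Complete-case analysis is used if under 5% is missing. Likewise, "if the treatment dummy variable is not significant then data are 'missing experimentally at random' (MEAR) and a complete case analysis is appropriate". The remedial steps, which include setting all missing outcomes to 1 or all to 0, have one trigger: "Where outcomes are MENAR, we will explore several methods to reduce bias".

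The primary model in 10.3 is "a parsimonious model with treatment as the predictor of interest, and two baseline covariates used in the blocking design of the randomisation", namely risk score and LA. Section 5.2 allocates so that "every block of four contains two treatment households and two control", with blocks formed by sorting on risk within LA. Section 10.6 already plans the covariate-free fit as a sensitivity analysis: "we will repeat the main analysis but dropping all predictor variables apart from treatment".

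**The concern.** The comparison sets two treatment estimates from the same complete cases side by side, one with risk and LA in the model and one without. If missingness depends on the outcome in different ways in the two arms, the bias is in the data that both fits use, so both carry it. Agreement between them is then no evidence against it.

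The plan nonetheless attaches a formal statement that bias is unlikely. A biased primary estimate could be published with that statement beside it. The imputation extremes that might qualify it would not have been run, because they wait on a significant treatment coefficient in the missingness model.

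**Working it through.** **1. The plan's own scale.** Scenario C (9.2 and Table 7) has an effective n of 1,600, so 800 per arm, with two-sided alpha 0.05 and power 0.8. MDES = (1.960 + 0.842) × √[(p₁q₁ + p₂q₂)/800].
- Near a 50% base rate: 2.802 × √(0.50/800) = 2.802 × 0.0250 = 7.0pp.
- For 3% against 1%: 2.802 × √[(0.0291 + 0.0099)/800] = 2.802 × 0.00698 = 2.0pp.

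This reproduces the stated 2–7pp.

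**2. An example by hand.** Take a 50% base rate (footnote to Figure 3), the planned 20% attrition in each arm, and no true effect. Ask what produces a spurious −7pp, that is, observed rates of 46.5% and 53.5%. Per 100 households randomised to each arm, 80 are observed.
- Treatment: 0.465 × 80 = 37.2 events observed, so 50 − 37.2 = 12.8 of the 20 missing are events (64%).
- Control: 0.535 × 80 = 42.8 events observed, so 7.2 of the 20 missing are events (36%).

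Each arm loses 20%, so the treatment coefficient in the missingness model is expected to be about zero. If risk and LA explain no outcome variance, as 9.1 assumes for planning, removing them leaves the −7pp essentially where it was.

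The extremes in 10.8 do not expose this either. All 1s gives 57.2 − 62.8 = −5.6pp, and all 0s gives 37.2 − 42.8 = −5.6pp. Arm-opposite extremes give 57.2 − 42.8 = +14.4pp and 37.2 − 62.8 = −25.6pp, a range that contains the true value of zero.

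**3. Simulation.** Inputs from the protocol: three LAs × 500 households (Test Valley is outside the primary model, 5.2), risk-sorted blocks of four split 2:2, and the 10.3 model against treatment alone. Assumed: the slope of outcome on risk (log-odds per SD), the missingness mechanisms, and the reading of similarity. There were 600 runs per setting, read only where a blocking variable was significant and treatment was not. Bias is the complete-case estimate minus the full-data estimate.

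| Setting | Missingness | Bias (pp) | Mean gap between fits (pp) | Fits within 2pp | Same significance verdict |
|---|---|---|---|---|---|
| slope 0, about 20% missing, null | risk/LA only | 0.0 | 0.13 | 100% | 99.3% |
| same | outcome by arm | −9.4 | 0.17 | 100% | 99.1% |
| slope 0.3, about 10% missing, null | risk/LA only | 0.0 | 0.13 | 100% | 99.6% |
| same | outcome by arm | −4.8 | 0.19 | 100% | 97.5% |
| slope 0.7, about 10% missing, null | risk/LA only | 0.0 | 0.23 | 100% | 98.6% |
| same | outcome by arm | −4.4 | 0.58 | 100% | 96.3% |
| slope 0.5, true −7pp, about 20% missing | risk/LA only | +0.1 | 0.26 | 100% | 96.2% |
| same | outcome by arm | +9.0 | 0.66 | 100% | 96.7% |

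At about 20% missing under the null, slopes of 0.3 and 0.7 gave biases of 9.2 and 8.4pp. Across slopes 0 to 0.7 the false-significance rate was 84–91%, the fits agreed within 2pp in 97–100% of runs, and the treatment test in the missingness model missed the mechanism in 91–95%.

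A second set of runs, at 16–18% missing, gave agreement within half a standard error in 95–100% and within one standard error in 100%. That held both with no bias and with biases of 4 to 11pp.

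**4. Where the fits separate.**
- Strong score (slope 1.2), outcome-by-arm missingness, 7pp bias: within 2pp in only 27%, though within one standard error in 100%.
- Slope 1.0 with the strong mechanism (±0.7 log-odds): within 2pp in 49%.
- Missingness depending on arm × risk (slope 0.7, 20% missing): the fits differ by about 3pp and agree within 2pp in 2%, yet the bias of the adjusted estimate is only −0.06pp.

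**The case against.** Several points against the concern stand. The sentence sits under description. The operative rules are the 5% threshold and the treatment coefficient, so deleting the sentence changes no analysis that is run. Section 9.2 expects few losses and calls 20% conservative, and 10.8 calls the risk of large-scale missingness generally low. Control households are not notified (8.2), so opt-outs should fall mainly in the treatment arm and, if sizeable, would show in the treatment coefficient and trigger the remedial steps. The outcome-by-arm mechanisms are assumed, and no check on observed data alone could exclude them.

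Three stronger readings are tempting, and the documents do not support them.
- *Blocking forces the two fits to agree.* Blocking balances the randomised sample, not the complete cases. Arm-by-risk missingness or a strong score can separate the fits.
- *The rule will regularly condemn sound analyses.* Dropping covariates does shift the odds ratio when there is a real effect. With a log-odds ratio of −0.5 and slope 1.0, the fits agree in only 19% of runs within half a standard error, but in 88% within one, and in 99.8–100% within 2pp. The plan sets no cut-off, so this reading rests mostly on the one chosen. The arm-by-risk case is the firmer example.
- *This check decides whether complete-case analysis is used.* A non-significant treatment coefficient already allows it.

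None of this rescues the inference. It is stated in the protocol itself and is not a detail left to an analysis plan. That no observed-data check can rule out such bias is a reason not to claim that one has.

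**Conclusion.** The inference is wrong as written. The comparison reflects mainly risk/LA imbalance between arms among complete cases, for which the primary model already adjusts, and non-collapsibility of the odds ratio. With a weak-to-moderate score, including the planning assumption in 9.1, a pass carries almost no information about outcome-related missingness. Pass rates were about the same with no bias and with an illustrative bias of 4–11pp at 16–18% missing, against an MDES of 2–7pp. With a strong score or arm-by-risk missingness the fits can diverge, in the latter case although the adjusted estimate is sound.

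The sizes rest on assumed mechanisms, slopes and cut-offs, and on missingness well above what the protocol expects. In the hand example, missing households must differ by 64% against 36% in risk to produce 7pp at 20% attrition. The finding is that the reassurance is unfounded. It does not show that this trial's estimate will be biased.

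**What to change.** In section 10.8, delete the inference from similar results to bias being unlikely. State instead that the primary model conditions on LA and risk, and so handles missingness that depends only on those.

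Run the all-1s and all-0s imputations whenever 5% or more of outcomes are missing, not only when treatment predicts missingness. Add the two arm-opposite patterns, or an arm-specific delta (tipping-point) analysis reporting how far the missing-outcome risks must differ between arms to change the conclusion. If the covariate-free fit from 10.6 is still compared, do so on the risk-difference scale and only as a check on specification.

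The cost is a short addendum and a small extra analysis on data already held. Arm-opposite bounds may be wide. Their width is the sum of the two arms' missing fractions: 5 + 5 = 10pp at 5% missing and 20 + 20 = 40pp at 20%. At the higher end the tipping-point form will be easier to interpret.
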